This study will evaluate the status of knee cartilage in 225 patients with varying degrees, and patterns, of knee OA using standing extension anteroposterior, 15 degrees flexion posteroanterior, 45 degrees flexion posteroanterior and valgus and varus stress views as well as MRI. These results will be compared to the gold standard imaging technique of stress views as well as to direct measurements of retrieved tissue in those patients who undergo knee replacement surgery. The sensitivity and specificity of each of the imaging techniques at predicting suitability for UKR will be calculated, the optimum imaging views proposed, and ultimately the results of this study will be used to develop a decision aid, based on optimum views, to help clinicians decide between likelihood of a patient being a candidate for UKR based on pre-operative x-ray and MRI findings.

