4. OBJECTIVES AND OUTCOME MEASURES/ENDPOINTS

Objectives	Outcome Measures
Primary Objective 
 • To assess the accuracy of different xray views of measuring joint space width within each compartment within the knee. 	Joint space width in the medial and lateral tibiofemoral compartments of the knee measured in mm.
Secondary Objectives 
 • To define the sensitivity and specificity of four different xray views at predicting bone on bone arthritis and joint space narrowing within each of the knee compartments and suitability for UKR. • To define the sensitivity and specificity of MRI at predicting suitability for UKR. • To assess the sensitivity and specificity of different xray techniques at inferring the status of soft tissue structures (anterior cruciate ligament and medial collateral ligament) within the arthritic knee. 	
A joint space width of 0mm will be classified as bone on bone arthritis, >0mm to <5mm will be classified as joint space narrowing and $\geq 5\text{mm}$ will be classified as full thickness cartilage. The sensitivity and specificity of each technique, at detecting each disease state in each compartment, compared to the gold standard of stress views will be recorded.
 
The sensitivity and specificity of MRI, compared to the gold standard of stress views, at predicting the status of each compartment will be recorded.
 
In patients proceeding to joint replacement as part of their standard clinical pathway the sensitivity and specificity of different xray techniques at inferring the status of soft tissue structures (anterior cruciate ligament and medial collateral ligament) within the arthritic knee will be compared to operative findings.

Tertiary Objectives 
 • To develop a decision aid to help clinicians decide between likelihood of a patient being a candidate for UKR based on pre-operative xray and MRI findings. 	The findings from this study will be used to develop a decision aid. The sensitivity and specificity of this decision aid will be calculated in the cohort of patients undergoing surgery using intra-operative audit findings as the gold standard.

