5. STUDY DESIGN

The study is a clinical investigation to determine the optimum xray technique for each compartment of the knee in patients aged over 50 years with knee arthritis.

All patients attending knee clinic will be informed about the study in advance. Those patients who meet the inclusion criteria will be referred to the research team in clinic. Screening would be performed in clinic and in those patients that do not have exclusion criteria further information about the study will be given and if the patients agree to participation valid informed consent will be taken. Screening and consent would take around 10 minutes. Two additional xray views will be taken alongside routine clinical views and would be expected to take a maximum of 10 additional minutes. An MRI scan would also be arranged, and this would take place at a separate time arranged at the patients convenience and would take around 30 minutes. No further research appointments would be performed. In patients who, as part of their clinical care, undergo knee replacement the excised joint surfaces, which are normally disposed of, would be retained and the degree and pattern of articular cartilage wear would be quantitatively evaluated before disposal. In addition an audit of the intra-operative findings would be performed.

Evaluation for inclusion and exclusion criteria would be via pre-tested standardised pro forma. A pain visual analogue scale would be used to assess for the presence and degree of pain during stress views. Xray images would be measured using custom measuring software (Matlab, Massachusetts , USA), MRI images would be measured using a segmentation method that has previously been described (Solidworks, Massachusetts , USA). Intra-operative audit of joint surfaces and soft tissue structures would be recorded on a standardised, pre-tested pro forma. Retrieved intra-operative samples of the joint surface would be scored using a validated technique, digitally photographed and surface geometry measured using a 3D laser scanner.

A flow chart of the study can be seen in Appendix A.

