7. STUDY PROCEDURES

- Screening and consent (performed at clinic appointment) - 10 minutes
- Standard Clinical Xrays
 - Standing anteroposterior view
 - Lateral view
 - Patellofemoral view
 - Valgus stress view (clinician performed or using validated device)
 - Varus stress view (clinician performed or using validated device)
- Research xrays (performed at the same time as routine clinical xrays) – 10 minutes
 - Standing posteroanterior (PA) view 15 degrees flexion
 - Standing posteroanterior (PA) view 45 degrees flexion
- MRI (performed during a separate appointment at the patients convenience) – 30 minutes
- Measuring of routinely retrieved joint surface cartilage (performed in research laboratory)

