10. STATISTICS AND ANALYSIS

10.1. Description of Statistical Methods

Joint space width of each of the compartments will be measured on each routine and research xray views taken using a standardised technique using custom software (Matlab, Massachusetts, USA). To compare the accuracy and agreement of different radiological views at measuring joint space width statistical methods for assessing agreement between two methods of clinical measurement as described by Bland and Altman will be used with stress views defined as the gold standard for comparison [12, 13].

For the secondary outcomes each of the compartments on each of the xray views will be classified as demonstrating bone on bone arthritis, full thickness cartilage or narrowing of joint space width. The sensitivity and specificity of each of the views at predicting each of these disease states will be compared with stress views which will be defined as the gold standard. The sensitivity and specificity of each of the views at predicting suitability for UKR will be calculated based on pre-defined indications of UKR.

The sensitivity and specificity of MRI at predicting suitability for UKR, based on pre-defined xray derived indications as the gold standard will be calculated.

The sensitivity and specificity of different xray techniques at inferring the status of soft tissue structures (anterior cruciate ligament and medial collateral ligament) within the arthritic knee will be evaluated against both MRI and intra-operative findings.

A decision aid will be developed based on the findings of this research and the sensitivity and specificity of this decision aid at predicting suitability for UKR will be calculated. Further work will then be performed to validate this scoring system.

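### Section 3 promises a comparison with retrieved tissue, but no analysis of joint space width, compartment state or MRI uses it, so for these outcomes stress-view accuracy cannot be measured

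*Combined protocol and SAP*

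**What the plan says.** Section 3 (Background and Rationale) says that the imaging results will be compared with stress views "as well as to direct measurements of retrieved tissue in those patients who undergo knee replacement surgery". Section 5 carries this into the design: for excised joint surfaces "the degree and pattern of articular cartilage wear would be quantitatively evaluated before disposal", by a validated score, photographs and a 3D laser scan, and operative findings are audited. Sections 7 and 8 list the tissue work, section 8 adds the audit of joint surface and ligaments, and section 7.3 treats tissue as valid only when surgery falls within 6 months of screening.

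The analysis sections name other references:

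- Joint space width: section 10.1 uses Bland-Altman agreement with stress views.
- Compartment state: section 10.1 says that accuracy at "predicting each of these disease states will be compared with stress views which will be defined as the gold standard".
- MRI: section 4 lists "The sensitivity and specificity of MRI, compared to the gold standard of stress views, at predicting the status of each compartment"; section 10.1 scores MRI for suitability for unicompartmental replacement (UKR) "based on pre-defined xray derived indications as the gold standard".
- UKR suitability by view: accuracy at "predicting suitability for UKR will be calculated based on pre-defined indications of UKR".
- Decision aid: section 4 scores it in operated patients "using intra-operative audit findings as the gold standard".
- Ligament status: operative findings in section 4; MRI and operative findings in section 10.1.

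Section 3 gives a reason for choosing stress views: they are the accepted standard and underlie the long-term UKR outcome studies. It also cites one study in which wide lateral stress-view spaces went with intact cartilage at surgery, and one that found poor correlation between valgus stress width and operative grade.

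**The concern.** If stress views define the truth for compartment state, their own sensitivity and specificity are 100% by construction. Any disagreement counts against the other view, even where that view is right and the stress view wrong. The study aims to propose optimum views and build a decision aid, so whether a simpler view or MRI reflects cartilage as well as stress views do, or better, is a natural question. The tissue and audit data could partly answer it, but no analysis is specified. If it is left open, the tissue may go unused, or the mapping from wear score to disease state may be chosen after the data are seen.

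The UKR-suitability references also differ across views, MRI and decision aid, so their accuracies would not be directly comparable.

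**Working it through.** **1. References side by side**

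| Outcome | Section 4 | Section 10.1 | Retrieved tissue used? |
|---|---|---|---|
| Joint space width | none named | stress views | no |
| Compartment state, by view | stress views | stress views | no |
| MRI | stress views | x-ray-derived UKR indications | no |
| UKR suitability, by view | none separate | indications, not spelled out | no |
| Ligament status | operative findings | MRI and operative findings | no |
| Decision aid | intra-operative audit | none named | no |

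Section 10.3 adds nothing on tissue.

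**2. The plan's own figure (section 10.2)**

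Effect size 0.63/1.1 = 0.57. A two-sided two-sample formula gives 2 × (1.960 + 0.842)² / 0.57² = 48.3, so 49 per group and 98 in total, against the stated 100. Then 100/0.5 = 200 and 200 + 25 = 225, exactly as stated. Dividing by the 50% surgery rate is needed only if about 100 operated patients are required, yet no joint-space or compartment analysis in section 10.1 uses that subset.

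Expected operated patients: 200 × 0.5 = 100 to 225 × 0.5 = 112.5. These are expectations, not maxima, and come before the 6-month window.

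**3. Effect of an imperfect reference**

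Assumptions, none from the documents: one state against the rest, prevalence 30%, stress-view sensitivity and specificity both r, errors independent given the true state. For an error-free view, apparent sensitivity is the reference's positive predictive value (PPV) and apparent specificity its negative predictive value (NPV).

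- r = 0.85: 0.255/(0.255 + 0.105) = 0.708; 0.595/(0.595 + 0.045) = 0.930.
- r = 0.90: 0.27/(0.27 + 0.07) = 0.794; 0.63/(0.63 + 0.03) = 0.955.
- At 50% prevalence both measures equal r, that is 0.85 and 0.90.

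With independent errors, apparent Youden index = (PPV + NPV − 1) × true Youden index. The factor is 0.638 (r = 0.85) or 0.749 (r = 0.90) and is the same for every view, so ranking among non-stress views is preserved.

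**4. When that ranking can fail**

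Suppose a 90%/90% view has errors correlated ρ with those of stress views, equally in both disease groups. Its apparent Youden index rises by ρ√(0.9 × 0.1 × r(1 − r)) / [P(1 − P)], where P is the stress-positive share (0.36 or 0.34).

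- r = 0.85: a 95%/95% independent-error view scores 0.638 × 0.90 = 0.574 and the 90%/90% view 0.638 × 0.80 = 0.510. They tie at ρ = 0.137.
- r = 0.90: 0.674 against 0.599. They tie at ρ = 0.187.

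The documents do not say whether errors correlate.

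**5. Precision of a subset analysis (Wilson 95% intervals, 30% prevalence)**

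| Operated | Sensitivity | Specificity |
|---|---|---|
| 100 | 26/30 = 87% (70% to 95%) | 60/70 = 86% (76% to 92%) |
| 50 | 13/15 = 87% (62% to 96%) | 30/35 = 86% (71% to 94%) |

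**6. Selection into surgery**

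Let true stress-view accuracy be 85%/85%, with shares v1 of stress-positive and v0 of stress-negative patients operated on. Observed sensitivity = 0.85v1/(0.85v1 + 0.15v0); observed specificity = 0.85v0/(0.85v0 + 0.15v1).

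- 60% and 40%: 89%/79%.
- 70% and 30%: 93%/71%.

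When surgery depends only on the stress-view result, the Begg-Greenes correction recovers the truth. PPV (0.708) and the diseased share among stress-negatives (0.070) are unaffected by selection, so sensitivity = 0.708 × 0.36 / (0.708 × 0.36 + 0.070 × 0.64) = 0.255/0.300 = 0.85. Specificity likewise returns to 0.85.

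**The case against.** **Stress views are the clinical standard.** Section 3 gives a reasoned case for them, and agreement with them is a legitimate question. This stands: the stress-view analyses should be kept, and the primary Bland-Altman analysis does not change. Wear scores and laser scans are not millimetres of joint space.

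**Operative references already exist.** They do for ligament status and, in section 4, for the decision aid. A reader might infer that stress-view accuracy is measured nowhere. That goes too far: the ligament analysis covers different x-ray techniques and could include stress views. The decision-aid analysis, however, tests the aid and not stress views, and uses the audit rather than the tissue.

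**Stress views may be good.** A reader might infer from the poor-correlation study that they are inaccurate. The documents cite one study on each side and do not settle it. Nor do they show that UKR suitability by view is scored circularly; its reference is undefined.

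**The views can still be ranked.** This is true if errors are independent, so it cannot be said that the plan fails to compare the non-stress views.

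**The operated subset is small and selected.** This stands as a limitation. Section 11.2 blinds the image evaluator, but nothing states that the operative audit is blinded to the routine stress views, so it may favour them. The type of reference (tissue or audit) may also follow the operation chosen, which stress views inform.

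**The fix strains blinding.** Section 10.3 blinds the statistical analysis to treatment outcome, and an operated-only subset reveals who had surgery. The planned ligament and decision-aid analyses already do so in part, but the amendment must address it.

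**Conclusion.** The concern holds for joint space width, compartment state and MRI. A comparison is promised and its data collected, but the analysis sections give it no place. For these outcomes the plan can show agreement with stress views. It cannot show how accurate stress views are, or that a view or MRI matches cartilage better. For UKR suitability the reference is unclear for the views, x-ray-derived for MRI and operative for the decision aid.

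Confidence is high for the omission. The numerical effect is illustrative only, because accuracy, prevalence and error correlation are all assumed. The point should be fixed; it does not invalidate the primary analysis.

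**What to change.** Add to section 10.1 a secondary analysis, in patients operated within 6 months of screening, of the sensitivity and specificity of every view (stress views included) and MRI for compartment cartilage state.

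- **Reference:** retrieved tissue where the surface was excised, the intra-operative audit otherwise (for example the retained compartment after UKR). Report by reference type.
- **Mapping:** before data are seen, fix how tissue score or audit grade maps to the disease states. The documents give no mapping; at minimum full thickness, partial loss and exposed bone are needed. Confirm that the audit pro forma grades each compartment.
- **UKR suitability:** in this subset use one intra-operative reference for views, MRI and decision aid.
- **Blinding:** score tissue blinded to imaging. Reconcile with section 10.3 by stating that image measurement and tissue scoring stay blinded, while the analyst necessarily knows who was operated on in this subset.
- **All patients:** keep the stress-view analyses and describe them as agreement with stress views.
- **Sensitivity analysis:** a Begg-Greenes estimate using the baseline stress-view result can be given, assuming that surgery depends only on recorded findings. Section 7.4 records the stress x-rays, but symptoms in general and patient preference are not listed as recorded, so the assumption may fail.
- **Limitations to report:** lower precision, verification of operated patients only, and an audit not stated to be blinded to stress views.

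The cost is modest: no new patients, visits or images, but the mapping needs real work. If the analysis is not wanted, remove the promise from section 3 and limit conclusions to agreement with stress views.

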8. INTERVENTIONS

In addition to the standard clinical imaging protocol described above trial participants will undergo:

- 15 degrees flexion postero-anterior view
- 45 degrees flexion postero-anterior view
- MRI knee without contrast

In those patients undergoing surgery as part of their routine clinical management:

- Intra-operative audit of joint surface and status of ligaments within the knee
- Assessment of retrieved samples of joint surface that would otherwise be disposed of

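### Sections 4 and 10.1 name different references for ACL and MCL status, and MRI ligament status is never checked against the operative finding

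*Combined protocol and SAP*

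**What the plan says.** In the combined protocol and SAP, the section 4 outcome table limits the ligament outcome to a defined group, "In patients proceeding to joint replacement as part of their standard clinical pathway", and states that x-ray inference of ACL and MCL status "within the arthritic knee will be compared to operative findings". Section 10.1 takes up the same objective and says that it "within the arthritic knee will be evaluated against both MRI and intra-operative findings". That sentence names no population and no order of precedence between the two references.

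MRI accuracy is planned for two other targets. Section 4 covers compartments: "The sensitivity and specificity of MRI, compared to the gold standard of stress views, at predicting the status of each compartment will be recorded". Section 10.1 covers suitability for unicompartmental knee replacement (UKR): "The sensitivity and specificity of MRI at predicting suitability for UKR, based on pre-defined xray derived indications as the gold standard will be calculated". Neither concerns ligaments.

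On data collection, section 8 lists, for patients who have surgery, "Intra-operative audit of joint surface and status of ligaments within the knee", and section 5 says this is recorded on a standardised, pre-tested form. For MRI, section 5 says "MRI images would be measured using a segmentation method that has previously been described". The documents give no rule for grading a ligament on MRI.

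**The concern.** The two sections leave open which comparison answers the secondary objective on soft tissue structures. One of the two references, MRI, is used to judge x-ray ligament inference without any planned check of how well it reads ligaments itself.

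Sensitivity and specificity have their usual meaning only when the reference is close to the truth. When ligament damage is uncommon, even a modest false-positive rate in the reference can fill the reference-positive group with intact ligaments. The figure labelled x-ray sensitivity then partly describes MRI error. Section 6.3 excludes previous ACL injury or reconstruction, which may lower the prevalence of ACL damage and make this more likely. If the two comparisons gave different answers, no planned analysis would show how much of the gap comes from MRI error.

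**Working it through.** **The plan's own figures.** The documents give no figure for the ligament analysis. The one figure that can be recomputed is the sample size in section 10.2. A two-group t-test with effect size 0.57, power 0.80 and two-sided alpha 0.05 (sidedness assumed) needs 50 per group, 100 in total, and 100/0.50 + 25 = 225. It reproduces, but it concerns joint space width and does not bear on this point.

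**The sections side by side.**

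| | Section 4 | Section 10.1 |
|---|---|---|
| Reference for ACL and MCL | Operative findings | MRI and intra-operative findings |
| Population | Patients proceeding to joint replacement | Not stated |
| MRI accuracy checked for | Compartment status | UKR suitability |
| MRI ligament status against surgery | Not planned | Not planned |

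**Effect of an imperfect reference.** All inputs are assumed, because the documents give no prevalence and no ligament accuracy for x-ray or MRI. Let p be the prevalence of ligament damage, SeM and SpM the MRI sensitivity and specificity, and SeX = 0.80 and SpX = 0.90 the true x-ray values. With errors independent given true status:

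- Apparent sensitivity = [p·SeM·SeX + (1−p)(1−SpM)(1−SpX)] / [p·SeM + (1−p)(1−SpM)]
- Apparent specificity = [p(1−SeM)(1−SeX) + (1−p)·SpM·SpX] / [p(1−SeM) + (1−p)·SpM]

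Worked case, p = 0.20 and MRI 0.90/0.90: the share of MRI positives truly damaged is 0.18/(0.18 + 0.08) = 0.692. Apparent sensitivity is 0.692 × 0.80 + 0.308 × 0.10 = 0.58.

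| MRI sensitivity = specificity | Apparent sensitivity, p = 0.20 | Apparent sensitivity, p = 0.10 |
|---|---|---|
| 1.00 | 0.80 | 0.80 |
| 0.95 | 0.68 | 0.58 |
| 0.90 | 0.58 | 0.45 |
| 0.80 | 0.45 | 0.32 |

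Apparent specificity moves much less. Across the six imperfect cases it runs from 0.584/0.68 = 0.86 (p = 0.20, MRI 0.80/0.80) to 0.90 (p = 0.10, MRI 0.95/0.95).

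**Dropping independence.** Suppose instead that x-ray and MRI errors overlap as much as possible, with p = 0.10.

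- MRI 0.90/0.90: apparent sensitivity is (0.1 × 0.80 + 0.9 × 0.10)/0.18 = 0.94, above the true 0.80.
- MRI 0.80/0.80: it is (0.08 + 0.09)/0.26 = 0.65, still below.

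The direction is therefore not fixed.

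**What a check could deliver.** Section 10.2 expects 50% of patients to have surgery: 0.50 × 225 = 112.5, about 112. At an assumed prevalence of 10% to 20%, that is 11 to 22 damaged ligaments of each kind. For an MRI sensitivity of 0.90, the 95% half-width is 1.96 × √(0.9 × 0.1/11) = 0.18, or 1.96 × √(0.9 × 0.1/22) = 0.13.

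**The case against.** The strongest reply is that MRI is only an additional comparator. Section 4 names operative findings for this outcome, and the decision aid also takes intra-operative audit as its gold standard. Section 10.1 uses that term for stress views and x-ray derived indications, but not for MRI in the ligament sentence. The operative comparison stays in the plan and MRI error does not touch it. This stands, and it limits the damage. It does not remove the problem, because section 10.1 still reports sensitivity and specificity against MRI, on an equal footing with surgery.

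Three stronger readings are tempting, and the documents do not support them.

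- *The MRI-based result would rest on about twice as many patients, with a different case mix.* Section 8 schedules MRI for all participants, so a reader might infer this. But section 10.1 states no population, and the only one given for this outcome is the operated group in section 4. Under that restriction both references apply to the same knees.
- *MRI is itself on trial here, so it cannot be a reference.* Section 4 does set out "To define the sensitivity and specificity of MRI at predicting suitability for UKR", but that concerns UKR suitability, and the other MRI analysis concerns compartments. MRI is not an index test for ligaments in this plan.
- *X-ray sensitivity will be understated.* That needs independent errors. The bias is zero if MRI is perfect and can be upward if errors are shared.

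It is also fair to say that the operative finding may not be error-free. Sections 10.3 and 11.2 blind the statistical analysis and the image evaluator, but nothing blinds the operative audit to imaging. An operated-only reference also leaves out unoperated patients, so keeping MRI as a labelled comparator is legitimate.

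**Conclusion.** The point holds as an inconsistency between sections 4 and 10.1 together with a missing check. Followed as written, section 10.1 would report x-ray sensitivity and specificity against a reference whose ligament accuracy this study could examine but does not plan to.

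The consequence is conditional on MRI being imperfect for ligaments, which the documents neither show nor rule out. In the illustration with independent errors, apparent sensitivity falls from 0.80 to between 0.32 and 0.68, while specificity stays within about 0.04 of the true 0.90. These values show how large the bias could be and are not an estimate of it.

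This is worth correcting because the repair is cheap, but its reach is limited to one secondary objective. The primary joint space width analysis, the sample size and the operative ligament comparison are unaffected.

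**What to change.** Amend section 10.1 as follows.

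1. Match section 4: the intra-operative finding is the reference standard for ACL and MCL status, in patients who have joint replacement.
2. In those operated knees, add one 2x2 table per ligament of MRI status against the intra-operative finding, with confidence intervals. State beforehand how a ligament is classified on MRI.
3. State the population for the x-ray versus MRI comparison and report it as positive and negative agreement, not as sensitivity and specificity. The symmetric forms, 2a/(2a+b+c) and 2d/(2d+b+c), with a and d the concordant positive and negative counts and b and c the discordant counts, treat neither test as the truth.
4. Do not pool the two references in one estimate.

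It may be tempting to adjust x-ray accuracy in all participants using MRI error rates from the operated knees. That should not be done: it assumes the rates carry over to unoperated knees, and it would rest on only about 11 to 22 damaged ligaments of each kind at the assumed prevalences.

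The cost is a change of wording and two extra tables from data already planned. The downside is that ligament accuracy rests on the operated patients only, about 112 of 225, so the estimates would be less precise than in the full cohort and would apply to that group.

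### The decision aid is built from this study's results and scored in the study's own operated patients with no internal validation, so its reported accuracy is apparent for any part chosen from those data

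*Combined protocol and SAP*

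**What the plan says.** On development, Section 3 says "the results of this study will be used to develop a decision aid, based on optimum views". Section 5 gives the purpose of the study: "The study is a clinical investigation to determine the optimum xray technique for each compartment of the knee". The choice of views is therefore a product of the study's data, made compartment by compartment.

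On scoring, Section 4 says "The sensitivity and specificity of this decision aid will be calculated in the cohort of patients undergoing surgery". The reference standard for this is the surgeon's record at operation, in the plan's words "using intra-operative audit findings as the gold standard". Section 10.1 repeats the sequence of developing and then scoring: "A decision aid will be developed based on the findings of this research and the sensitivity and specificity of this decision aid" are to be calculated for suitability for UKR. It adds that further work will later validate the scoring system, without giving a method, sample or date.

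Several elements are set in advance. Section 4 fixes the joint-space classes at 0 mm, above 0 to below 5 mm, and 5 mm or more. In Section 10.1 the disease states on each view are "compared with stress views which will be defined as the gold standard", and the accuracy of the views "at predicting suitability for UKR will be calculated based on pre-defined indications of UKR". Section 3 also gives a prior rationale for the 15 and 45 degree views.

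Operative data enter as well. Section 3 compares the imaging results with stress views "as well as to direct measurements of retrieved tissue in those patients who undergo knee replacement surgery", and Section 10.1 evaluates x-ray inference of ligament status against intra-operative findings.

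**The concern.** When part of a diagnostic rule is chosen because it performed best in a set of patients, its accuracy in those same patients is on average somewhat too favourable. The operated patients on whom this aid is scored are a subset of those from whom the optimum views are identified. Nothing in the plan separates the two steps or adjusts for the overlap.

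Sensitivity and specificity are the stated outcome measure for the aid (tertiary in Section 4, listed as secondary in the Synopsis), and Section 3 presents the aid as the study's ultimate use. As written, a reader of the results could not tell whether the two figures are free of selection in overlapping patients.

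**Working it through.** **1. How many patients score the aid.** The plan states no figure for the aid, so the number must come from Section 10.2. The effect size is 0.63/1.1 = 0.57. The two-group normal formula, n per group = 2(1.960 + 0.842)²/0.57², gives 48.3, rounded up to 49, or 98 in total (two-sided 0.05, power 0.8). This agrees with the stated 100. Then 100/0.5 = 200, and 200 + 25 = 225, as stated. Expected operated patients are 225 × 0.5 = 112.5, or 200 × 0.5 = 100 without the x-ray allowance: about 100 to 112.

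**2. What overlaps.**

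| Part of the aid | Source | Open to optimism? |
|---|---|---|
| Joint-space classes | Fixed in Section 4 | No |
| Indications for UKR | Described as pre-defined in 10.1 | No, as stated |
| Views used in each compartment | This study's results (Sections 3 and 5) | Yes |
| How x-ray and MRI findings are combined | Not described | Cannot be told |

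**3. Size if only the views are chosen.** Optimism is the apparent value in the operated patients minus the true value of the same chosen views in new patients. It was simulated, and every setting below is an assumption:
- Candidates: three non-stress x-ray views, or four options with MRI. One is chosen per compartment by the highest Youden index (sensitivity + specificity − 1) against stress views.
- Suitability: cartilage loss medially and preserved cartilage laterally (simplified from Section 3), true in 48 to 63% of operated patients.
- Views: separation 1.6 or 2.2 SD, error correlation between views 0.2 to 0.8, views equal or differing by up to 0.3 SD either way.
- Stress reference: wrong in 10 to 20%, with errors independent of the views or shared with them.
- Surgery: unrelated to disease, or 65% against 27.5% by medial bone-on-bone status.
- Replicates: 1,200 per setting, with the extremes rerun at 6,000.

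Results, in percentage points:
- Range over settings, per measure: -0.7 to 2.3.
- Mean for sensitivity/specificity: 1.0/1.0 with surgery unrelated to disease, 0.9/1.2 with surgery related to it.
- Example (200 patients, three equal views, 2.2 SD, correlation 0.5): apparent 0.763/0.912, true 0.747/0.897. Optimism is 0.763 − 0.747 = 1.6 points and 0.912 − 0.897 = 1.5 points.
- Rule fixed wholly in advance: 0 by construction.

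**4. Size beside sampling error.** Suppose about 50 of 100 operated patients are suitable and 40 are detected. The 95% Wilson interval is [p + z²/2n ± z√(p(1−p)/n + z²/4n²)]/(1 + z²/n). With p = 0.8, n = 50 and z = 1.96 this is (0.8384 ± 0.1173)/1.0768 = 0.67 to 0.89, about 22 points wide. An optimism of about 1 point is small beside it, but an interval around an apparent estimate does not remove the shift.

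**5. Does the correction work?** In one simulated setting with stress-chosen views, a bootstrap that repeated the selection rule moved 0.635/0.868 to 0.624/0.858, where the truth was 0.623/0.852. For sensitivity it removed 0.011 of 0.012 (92%). For specificity it removed 0.010 of 0.016 (63%). Pooled, that is 0.021 of 0.028 (75%). These shares come from rounded figures. The correction helps but is partial.

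**The case against.** The strongest reply is that the plan already treats this as a development stage. Section 10.1 places validation after the in-study calculation and nowhere calls the in-study figures validated. That stands: it would be wrong to infer that validation is never intended. The promise still neither corrects the figures that this study will report nor labels them.

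A second reply is that the documented case is minor. The classes are fixed, the indications pre-defined, and the views compared with stress views, while the aid is scored against a different reference. This also stands, and it is why the size is about 1 point. It reduces the optimism without removing the overlap in patients.

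A third reply is that Section 10.3 blinds the analysis to treatment outcome. That does not say the aid is settled before operative findings are seen, and the ligament analyses need those findings.

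A fourth reply is that the simulation is not this aid. It leaves stress views out of the candidates, although an aid might use them, and it ignores ligament status. That is fair. The figures show scale only.

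A reader might infer something much worse: that a score or cut-off is fitted to the operated patients. Under assumed settings, a logistic score with 6 or 8 inputs fitted to 100 to 112 patients gave roughly 3 to 11 points of optimism per measure. Choosing a cut-off in the scored data, with or without choosing among views, inflated sensitivity plus specificity by 0.07 to 0.17. The documents do not support that reading. No section describes estimated weights or cut-offs, Section 4 fixes the classes, and calling the aid a scoring system in 10.1 is at most a hint. Nor do they say that operative findings guide the choice of views. Neither possibility is excluded, so neither can be used to size the problem.

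**Conclusion.** The point holds as a minor one. The aid's sensitivity and specificity will be apparent performance for whatever part of it is chosen from this study's data, and the choice of views is one such part on the documents' own account. The size cannot be fixed from the documents. It is nil if the aid is wholly pre-specified, and about 0 to 2 points per measure (range -0.7 to 2.3, so not always favourable) if views alone are chosen against stress views with the fixed classes. It would be larger only if operative findings guide the choice or a score or cut-off is fitted. The primary Bland-Altman comparison of joint space width does not use the aid and is unaffected.

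**What to change.** Add a short paragraph to Section 10.1:
- Fix the rule for selecting views, and any weights or cut-offs, before operative findings are analysed. If every part of the aid is settled in advance, say so; no correction is then needed.
- Otherwise report the aid's sensitivity and specificity with 95% confidence intervals after bootstrap optimism correction. Each resample should be drawn from all participants, because the views are identified in the whole cohort, and should repeat the entire selection rule. Show the uncorrected figures alongside, labelled apparent.
- If any part is chosen by judgement and cannot be resampled, label the figures as apparent pending the later validation that Section 10.1 already foresees.

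The cost is a paragraph of text and a little computing. No further patients, images or visits are needed. The reported accuracy may be slightly less favourable, and the correction is only partial.
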